# **Using TMS to Increase Executive Function in Older Adults**

**NCT02767323**

## **Study Protocol**

**Date of Approval:**  
**01/19/2021**

Behavioral research on aging has mapped contrasting patterns of decline and stability in cognition across the adult lifespan. Both cross-sectional and longitudinal studies find robust declines in working memory (WM), which describes the storage and manipulation of temporary representations of information that was just experienced or just retrieved from long-term memory. The current proposal seeks to use a functionally-guided brain-stimulation (repetitive transcranial magnetic stimulation or rTMS) paradigm to modulate the working memory functions of the left dorsolateral prefrontal cortex (DLPFC) or left parietal cortex (PC). The research team carries the expectation that, active rTMS over the DLPFC and PC will improve WM performance compared to sham rTMS; and since older adults rely more heavily on prefrontal function than young adults, older adults will benefit more from DLPFC stimulation than the young. Differential rTMS modulation of WM performance between young and older groups will provide causal evidence for compensatory processing, and help fill out our understanding of the neural basis of sustained, successful performance in aging. While we have previously demonstrated WM effects from stimulating the lateral occipital cortex (LOC), a specific region within the occipital PC, a finding of relative enhancement of executive processing with PFC stimulation- an enhancement that is long lasting and that transfers to executive processing beyond WM- is a key to development of noninvasive brain stimulation treatment of cognitive deficits, as this more frontal brain region is closely associated with neuroplastic abilities like executive processing. This will be tested through three aims, in which rTMS will be applied over the DLPFC (Aim 1a), the LPC (Aim 1b) or both the DLPFC and the LPFC in alternating blocks (Aim 1c). We have 3 key objectives:

**Primary Objective:** To evaluate the ability of rTMS applied to the DLPFC, the PC to enhance working memory performance in both younger and older adults.

**Primary Endpoint:** We expect performance enhancements between active and sham rTMS to PFC or PC to increase as the task becomes more difficult, as executive control processes are centered in this region.

### Design and Procedures

This blinded, sham-controlled trial will feature a mixed model cross-over design, with rTMS Type (active, sham), Difficulty Level, Stimulation Location (DLPFC, PC), and Group (Young, Older adults) as factors. As such, this design reflects the fact that all subjects receive both active and sham rTMS applied to up to two different scalp locations during a WM task at up to three levels of difficulty. Study procedures are listed in **Table 1**. Up to thirty healthy young adults (age range: 18-35 years), thirty healthy older adults (age range: 55-80 years), will participate. In the initial session, which will take about 3 hours, participants will be consented and screened for the study, have a saliva sample taken, have TMS motor threshold determined, and then learn and practice the WM task. A structural and functional MRI will then be acquired within the screening visit or in a separate visit dependent on the participant's schedule. Cortical locations within PC and PFC to be used as targets for rTMS will be chosen from an analysis of subject-specific fMRI activations. Following the MRI, participants will take part in up to 5 sessions of rTMS (4 visits in Aim 1 and Aim 1b; and two visits in Aim 1c), each lasting up to 3 hours. TMS sessions will begin ~1 week after the MRI Session, to allow for time to process the imaging data, and within a 3-month period (Mondays thru Fridays), aiming to occur at the same time each day (+/- 2-3 hours for scheduling flexibility). Up to 5 rTMS sessions (involving active or sham rTMS and DLPFC (Aim 1a, Aim 1c), or PC targets (Aim 1b, Aim 1c) will use coil locations and rTMS device intensities based on realistic head modeling. Participants will report number of hours slept the previous night at each visit.

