### Subject Screening

Normal right-handed volunteers will be recruited from the community. At the beginning of their first visit to the rTMS laboratory, they will undergo neuropsychological screening (such the MINI, NACC, PHQ-9, CDR and/or BDI) and a urine test. If they pass the screening procedure, they will proceed to the rTMS lab, where

they will learn and practice the memory tasks used in the study (about 2 hrs), and will have a short session of rTMS (about 0.5 hr), in order to acclimate them to rTMS and to obtain right and left hand motor thresholds for future dosing of rTMS.

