#### WM TASKS:

Two WM tasks will be performed a Delayed Response Alphabetization task (DRAT, Aim 1a, 1b, 1c) involving both maintenance and manipulation of information and a Delayed Response Maintenance Task (DRMT, Aim 1c) that only involved maintenance. Our implementation of the WM task for MRI consists of up to 10 runs of approximately 10-minute long letter-presenting blocks. Each trial begins with the presentation of a fixation cross during 5 seconds followed by the presentation of up to 9 uppercase letters arranged in a line. In the case where fewer letters are presented, all other positions are filled with asterisks. Stimuli are presented for up to three seconds before the screen is cleared. After a retention interval of 5 seconds, a probe stimulus is presented in the center of the screen for four seconds. The probe consists of the combination of a letter and a number, and which subjects are asked to answer. During this period subjects must press one of three keys indicating whether the number matches the position of the letter in the reorganized alphabetical order for the DRAT; or the serial position of the letter for the DRMT (Valid trials); or if the number does not match the letter position (Invalid trials); or if the letter did not belong to the array of letters (New, Aim 1a and 1b). Feedback is provided, at the end of each block as the overall accuracy. Tasks are performed with 1 (Hard, Aim 1c first cohort), 2 (Easy and Hard, Aim 1b and Aim 1c second cohort), or 3 (Easy, Medium, and Hard: Aim 1a) difficulty levels, defined as the number of letters presented on the screen and individually for each subject according to their performance during the screening visit. In rTMS sessions, the WM tasks will be run while stimulation is applied over the DLPFC (Aim 1a, Aim 1c) or the PC (Aim 1b, Aim 1c) either before the encoding (Aim 1a, Aim 1c) or during the delay period (Aim 1b, Aim 1c). Each block of trials will take about 10 minutes. To clarify all these conditions please refer to Figure 1 below.

	Group	Dosing	Timing	Site	Task	Difficulty	
Aim 1a	YA	100%rMT	Before the encoding	Frontal	DRAT	Easy	n= 29YA + 18 OA (6conditions/subj)
	OA	100%Eref 80%Eref	During the delay	Parietal	DRMT	Medium Hard	
Aim 1b	YA	100%rMT	Before the encoding	Frontal	DRAT	Easy	n= 15OA (4conditions/subj)
	OA	100%Eref 80%Eref	During the delay	Parietal	DRMT	Medium Hard	
Aim 1c Cohort 1	YA	100%rMT	Before the encoding	Frontal	DRAT	Easy	n= 15YA (4conditions/subj)

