#### **APPLICATION OF RTMS DURING WM TASK PERFORMANCE:**

The subject will be seated comfortably in a chair, facing a computer screen positioned in front of the subject for visual stimulus presentation. Earplugs will be worn to protect hearing. The participant's head may be held steady by a frame with a chin rest and the rTMS coil holder frame. A figure eight magnetic coil will be placed on the scalp and held in place with a coil fixing system supplied by MagVenture. This will be paired with the BrainSight tracking system which provides precise fMRI-guided rTMS coil placement for basic, translational, and clinical applications of rTMS. The BrainSight program enables the coil to be placed at precise cortical targets (chosen from the subject's fMRI activations from the WM task from the MRI session) on the individual's 3-dimensionally rendered brain MRI with less than one millimeter error, and enables the research team to dynamically move the coil to account for slight head movements while the subject performs the task. Five-second trains of 5 Hz rTMS will be administered at up to 130% of the individual's MT with the stimulating coil tangential to the scalp. Sham rTMS will be administered with a sham coil equipped with shielding to block magnetic field output but retain the auditory and some of the tactile aspects of active stimulation. rTMS administration will be controlled by an external computer and will be time-locked relative to stimulus presentation. A brief rTMS side effect rating scale and visual analog mood ratings will be administered before and after each rTMS block. There will be up to 12 blocks of trials per session, and each session will take about 2 hrs. Subjects' side-effects will be monitored closely. As indicated in the procedures section, side effects are assessed in a charted, structured interview both prior to and after the rTMS session. Subjects are instructed during the consent process and during the rTMS sessions about all known side effects. They are further instructed during consenting and additionally at the conclusion of the rTMS session to contact the principal investigator or study physician with any questions or concerns (including those that may arise after the experimental session has ended).

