**Imaging acquisition and preprocessing.** Three forms of structural images will be acquired: **1) full-brain high-resolution T1-weighted structural images** (inversion recovery prepared 3D SPGR) with full coverage of the head and neck, (TR = 500ms; TE = 20ms; FoV = 24cm^2; image matrix = 256x256; voxel size = 0.94 x 0.94 x 1mm), and **2) echo-planar (EPI) sensitivity encoding (SENSE) DWI images** with the same orientation (TR = 2000 ms; FoV = 24 cm^2; image matrix = 128; voxel size 0.94 x 0.94 x 1 mm; b-value = 1000 s/mm^2; 1 repetition; 36 diffusion-sensitizing directions). In addition, two forms of functional images will be collected: **1) for resting state EPI** functional imaging data, which will be used to estimate RSFA, we will acquire 24 slices parallel to the AC-PC plane using a BOLD-sensitive gradient-echo sequence with EPI k-space sampling, at TR of 2s (TE: 35ms; FOV: 25.6cm; voxel size: 63mm), and **2) event-related EPI**, which uses the same scan parameters and will measure the global reactivity to our Working Memory Task.

**TMS methods.** Coil targeting will be achieved using frameless stereotaxy (BrainSight: Rogue Research, Montreal). TMS is applied with a figure 8 coil based on 100% resting motor threshold (rMT), though TMS intensity will also be informed by E-field modeling (described below). TMS will be delivered consecutively over the individualized target region, based on the cortical site with the highest computed controllability (Network target) or parametric activity (Activity target), using a MagVenture stimulator. Neuronavigation (BrainSight, Rogue Research, Canada) and a robot (SmartMove, ANT, Netherlands) will be used to optimize the targeting. Brain atrophy could also reduce TMS effectiveness because it increases the distance between scalp and the cortex but this potential confound is addressed by adjusting TMS intensity using the E-field computation. In visits 3 to 6, participants will perform the Working Memory Task while active or electrical sham stimulation is delivered using an A/P Cool-B65 coil (MagVenture, Denmark). In a stimulation trial, twenty-five pulses of 5Hz

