Aim 1a: rTMS applied over the DLPFC either before the encoding or during the delay period of the Delayed Response Alphabetization Task (DRAT, a working memory task in which participants were asked to maintain and reorganize in alphabetical order an array of letter) will be performed by young and older healthy adults with three difficulty levels, during 4 rTMS visits. Since it is expected that Valid (trials in which the number matches the position of the letter in the reorganized alphabetical order) and Invalid (trials in which the number does not match the position of the letter) trials will lead to strong differences in accuracy, two ANOVAs will be performed separately on each trial condition, for reaction time and accuracy. The two ANOVAs will be conducted with Group (Younger or Older adults), as the between-subject factor; and Visit (Visit 3, Visit 4, Visit 5 and Visit 6), Difficulty (Easy, Medium, and Hard), Stimulation Timing (Pre and Post) and Stimulation Type (Active and Sham) as the within-subject factor. If no difference are found between the two groups, they will be collapsed and the ANOVA will be performed on the larger sample.

Aim 1b: rTMS applied over the PC during the delay period of the DRAT performed with two difficulty levels in older adults, comparing the effect of two stimulation intensities defined with electric field modeling (E-field). A repeated measure ANOVA will be performed with Task Condition (Valid and Invalid), Stimulation Type (Active and Sham), Stimulation Amplitude (80% and 100% Eref), and Task Difficulty (Easy and Hard).

Aim 1c: rTMS applied over the DLPFC and the PC in younger adults performing the DRAT and the Delayed Response Maintenance Task (DRMT, an additional WM task added to the design and involving only the maintenance of the array of letter). rTMS will be applied before the encoding period of the WM tasks, performed with either one difficulty level (Hard) or two difficulty levels (Easy and Hard) in younger adults. A repeated ANOVA will be conducted with Task Condition (Valid and Invalid), Difficulty levels (only for subjects who performed the task with Easy and Hard difficulty levels), WM task (DRAT and DRMT), Stimulation Site (DLPFC and PC), and Stimulation Type (Active and Sham).

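### The order of active and sham stimulation is not stated and no planned ANOVA models block position (nor visit in Aims 1b and 1c), so practice or fatigue drift can bias the active-sham main effect or inflate its error

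*Protocol*

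**What the plan says.** **Design.** Under Design and Procedures the protocol describes the trial thus: "This blinded, sham-controlled trial will feature a mixed model cross-over design, with rTMS Type (active, sham), Difficulty Level". The same section says that "all subjects receive both active and sham rTMS applied to up to two different scalp locations".

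**Order.** The TMS methods paragraph says: "In visits 3 to 6, participants will perform the Working Memory Task while active or electrical sham stimulation is delivered". It does not say whether the two types share a visit or which comes first. The one order statement in either document is in the protocol's introduction, where stimulation goes to "both the DLPFC and the LPFC in alternating blocks (Aim 1c". (The second site is named PC in the rest of the design text.) It concerns site only and gives no starting site. Figure 1 lists conditions per aim, not their order.

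**Exposure to drift.** In the section on applying rTMS: "There will be up to 12 blocks of trials per session". The WM Tasks section puts a block at about 10 minutes and adds: "Feedback is provided, at the end of each block as the overall accuracy". That sentence sits in a description that begins with the MRI version of the task.

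**Analysis.** The SAP's Aim 1a ANOVA has Group between participants. Within participants it has "Visit (Visit 3, Visit 4, Visit 5 and Visit 6), Difficulty (Easy, Medium, and Hard"), Stimulation Timing and Stimulation Type. Aim 1b has Task Condition, Type, Amplitude and Difficulty. Aim 1c has Task Condition, Difficulty (where two levels were run), Task, Site and Type. None has a block-position or sequence term, and Aims 1b and 1c have no Visit term.

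**The concern.** In a cross-over, active minus sham is a treatment effect only if the two conditions occupy comparable positions in time, or if the model accounts for position. With up to 12 blocks of about 10 minutes, performance may rise with practice or fall with fatigue.

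- If one condition tends to come later, that drift enters the active-sham main effect, which is what the Primary Objective asks about. The bias can create an effect or mask one.
- If order is balanced across participants but position is not modelled, the estimate is unbiased. The drift then goes into the error term, and the test is conservative and loses power.

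The first problem depends on facts the documents do not give. The second follows from the models as written whenever drift is present and participants differ in order.

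**Working it through.** The documents give no alpha, SD, effect size or power calculation, so there is no figure of theirs to reproduce.

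**Inputs from the documents**
- Up to 12 blocks per session (Protocol, rTMS application).
- Aim 1a: n = 29 + 18 = 47. Aim 1b: n = 15. Aim 1c: n = 15 (cohort 1) and n = 14 (cohort 2) (Protocol, Figure 1).

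**Assumptions**
- Two-sided 5% test, no true rTMS effect.
- 6 active (A) and 6 sham (S) blocks in the same session.
- Linear drift of b = 0.02, 0.05 or 0.10 per block, in SDs of the per-participant active-sham difference.

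**Step 1: offset between conditions** (mean active position minus mean sham position)
- All sham first: 9.5 − 3.5 = 6 blocks.
- Alternating, sham first: 7 − 6 = 1 block.
- SAAS three times: 6.5 − 6.5 = 0.

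**Step 2: false rejection.** Bias = b × offset. The paired t test (equivalent to the 1-df within-participant F) then has noncentrality b × offset × √n on n − 1 df. For example, with b = 0.05, offset 6 and n = 47, bias is 0.30 SD, noncentrality is 0.30 × √47 = 2.06, the critical value is 2.013 and rejection is 52%.

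| Offset | b | Bias (SD) | n=47 | n=15 | n=14 |
|---|---|---|---|---|---|
| 1 block | 0.02 | 0.02 | 5.2% | 5.1% | 5.1% |
| 1 block | 0.05 | 0.05 | 6.3% | 5.4% | 5.3% |
| 1 block | 0.10 | 0.10 | 10.3% | 6.5% | 6.4% |
| 6 blocks | 0.02 | 0.12 | 12.7% | 7.2% | 7.0% |
| 6 blocks | 0.05 | 0.30 | 52.1% | 19.2% | 18.0% |
| 6 blocks | 0.10 | 0.60 | 98.1% | 58.0% | 54.7% |

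A zero offset leaves 5%.

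**Step 3: order balanced but not modelled.** Let half the participants run all sham first and half all active first. Mean bias is 0, but each difference carries ±6b. At b = 0.10 the variance of the differences is about 1 + 0.6² = 1.36 times its proper value, so the estimated standard error is about √1.36 = 1.17 times too large. By simulation, size at b = 0.05 to 0.10 is 0.04 to 0.02 without an order term and 0.05 with one. At n = 14, b = 0.10 and an assumed true effect of 0.5 SD, power is 0.29 without the term and 0.41 with it.

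**Step 4: the Type-by-Difficulty endpoint.** Write the bias at each difficulty as slope × offset. The bias in the hard-minus-easy contrast of active minus sham is slope(hard) × offset(hard) − slope(easy) × offset(easy). It is zero when both slope and offset are the same at the two levels. Difficulty order is also unstated, so equality of the offsets cannot be confirmed.

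**The case against.** **Silence is not evidence of imbalance.** These are short documents, and a counterbalanced order may well have been used. This stands: a reader might infer that order was unbalanced, and nothing supports that. The missing block-position term does not depend on it.

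**Sharing a session is inferred.** Crossing Visit with Type in Aim 1a suggests that both types occur within a visit. Aims 1b and 1c give no such clue. If Type varied by visit, the confounding would be with visit, a block-position term would not help, and Aim 1a's Visit-by-Type crossing could not be estimated within participants. This stands, so the fix must cover both cases.

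**The primary endpoint is largely shielded.** A reader might infer that drift adds directly to it. Step 4 shows that an offset common to all difficulty levels cancels. The main effect, and so the Primary Objective, remains exposed.

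**Residual drift may be small.** At screening, "they will learn and practice the memory tasks used in the study (about 2 hrs"), and up to 10 MRI runs of about 10 minutes follow before any rTMS. Difficulty is also set individually. This should flatten learning, but it does not exclude fatigue or guarantee a plateau.

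**Large error rates need strong assumptions.** With a gain of 2 accuracy points per block, an SD of 4 to 6 points and active always one block later, rejection at n = 47 would be 61-92%. But four visits of 12 blocks have 47 steps, so that slope implies 47 × 2 = 94 points. Guessing among three keys to perfect accuracy spans only about 67. The slope could not persist, and that figure should not be used.

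**Alternation.** It concerns site in Aim 1c, not active versus sham, and limits the site offset to about one block. The documents also do not support a claim that order compromised the blinding.

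**Conclusion.** The point holds as a gap in the stated design together with an omission in the stated models. No order of active/sham, timing, amplitude or task is specified. No aim models block position, and Aims 1b and 1c do not model visit. The active-sham main effect can be biased in either direction if order is unbalanced, and is tested with inflated error if order is balanced across participants and drift exists. The Type-by-Difficulty endpoint is affected only if drift or imbalance differs by difficulty.

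The true size is unknown. Under the assumed drift, it runs from negligible with simple alternation to serious if all sham precedes all active. Nothing in the documents indicates that the extreme order was used. Stating the order is what would show where in that range the trial lies.

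**What to change.** 1. **Protocol, Design and Procedures.** State whether active and sham share a session. State that each participant receives a counterbalanced order generated before the first rTMS session, covering Type and difficulty in all aims, timing in Aim 1a, amplitude in Aim 1b, and starting site and task in Aim 1c. Balance it within aim and age group. If such an order was used, describing it closes this part.
2. **SAP, TMS data.** Fit each aim as a block-level mixed model with a participant random effect. Add Visit in Aims 1b and 1c, and linear block position within visit in all aims. Include at most a two-level order term (active first versus sham first). A full sequence factor would be close to inestimable in cohorts of 14 or 15. If Type varies by visit, Visit and the order term do this work and block position does not.
3. **Participants already run.** Use the recorded block order where available. The protocol says rTMS is computer-controlled but not that a log of order is kept, so state for how many participants it can be recovered.

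**Cost.** No extra visits or participants. The added terms use at most 2 df in Aim 1a (position, order), 3 + 1 + 1 = 5 in Aim 1b with four visits, and 1 + 1 + 1 = 3 in Aim 1c with two visits. There is also some work to prepare the order list and refit the models.

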**Table 1. TIMELINE OF STUDY PROCEDURES FOR MAJOR STUDY:**

Assessment	Screening Session	MRI Session	rTMS Sessions
1. Subject consent & screening	X		
2. Practice with WM task	X		
3. Structural MRI	(X)	X	
4. fMRI with WM task	(X)	X	
5. Motor Threshold	X		
6. WM task + rTMS			X
7. Side Effect Checklist			X
8. Visual Analog Scale			X

### Subject Screening

Normal right-handed volunteers will be recruited from the community. At the beginning of their first visit to the rTMS laboratory, they will undergo neuropsychological screening (such the MINI, NACC, PHQ-9, CDR and/or BDI) and a urine test. If they pass the screening procedure, they will proceed to the rTMS lab, where

they will learn and practice the memory tasks used in the study (about 2 hrs), and will have a short session of rTMS (about 0.5 hr), in order to acclimate them to rTMS and to obtain right and left hand motor thresholds for future dosing of rTMS.

